### **Prior Studies of pre-operative radiotherapy in prostate cancer assessing safety**

Duke University undertook a phase I dose escalation trial of pre-operative fractionated intensity modulated RT followed by prostatectomy (12). All patients were treated to the prostate and seminal vesicles to 39.6, 45, 50.4, and 54 Gy in fractions of 1.8 Gy. The pelvic nodes were also treated, but to a maximal dose of 45 Gy. No intraoperative morbidity was observed. Acute toxicity was limited to Grade 1 (GU and GI). Late toxicity, primarily GU, was within the range expected for adjuvant post-operative RT.

The conclusion was that 54 Gy is a safe dose for preoperative RT followed by prostatectomy.

Princess Margaret Hospital undertook a phase I trial of 15 patients for pre-operative RT followed by prostatectomy within four weeks of completing RT (15, 16). Conformal RT technique (one patient was treated with IMRT) was used to deliver 5 fractions of 5 Gy without image guidance. There were no intraoperative complications, no late GI toxicity. Two cases of long-term urinary incontinence were observed. Overall, GU toxicity was within the range expected for adjuvant post-operative RT.

Notably, our study would utilize modern image guidance and precise treatment volumes, which have been shown to reduce GU and GI toxicity in prostate radiotherapy as compared to conformal techniques.

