**Follow-up:**

- 0 to 4 weeks after the final fraction of radiation, patients will have approximately 60 mLs of blood drawn for serum translational biomarker research. Patients will also be evaluated by their physician and Adverse Events and Concomitant Medications will be assessed. EPIC and IPSS questionnaires will also be administered at this time.
- Patients are followed every three months ( $\pm$  4 weeks) for one year post surgery. At each follow-up visit, patients are evaluated for CTCAE (version 4.0) toxicity scores, and the EPIC and IPSS questionnaires will be administered. Blood draws (~5 mLs) to assess PSA are drawn at each of the follow-up visits unless PSA lab evaluations have already been done within 4 weeks of the study visit. In addition, at the 3 month and 6 month follow-up visits, approximately 60 mLs of blood will be drawn for serum translational biomarker study. After one year of follow-up, patients will be seen as per routine care.

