For comparison between post SBRT prostatectomy specimens and biopsy material pre-SBRT, average IntMax will be compared using a paired t-test or Wilcoxon signed-rank test (if the IntMax scores do not follow a normal distribution). For comparison between post SBRT prostatectomy specimens and archived material, average IntMax will be compared using a t-test or Wilcoxon rank-sum test (if the IntMax scores do not follow a normal distribution).

**RNA and DNA exome sequencing (secondary objective).** Quality control will be performed on the raw sequence data from RNA-seq experiments, which contain multiple short-read sequences with Phred quality score information using FastQC and FASTX-Toolkit. Bowtie2 will be used to align reads, which will then be mapped to the reference genome by TopHat2. Raw reads from exome sequencing will be aligned via BWA and converted to BAM format, and processed with the Genome Analysis Toolkit software package. Comparisons will be made to existing sequencing data (TCGA) for localized prostate tumors matched for histology and Gleason grade. Functional annotation will be performed using Gene Ontology, KEGG, and Reactome.

**Stopping Rules for Toxicity.** Prior studies evaluating RT prior to prostatectomy demonstrate safety of pre-operative RT at doses of up to 54 Gy in 30 fractions (12). It is anticipated that toxicity in this study will be low because our dose is selected based on the prior studies.

Nevertheless, our trial will be stopped for toxicity if any treatment related toxicity of CTCAE v4.0 grade 3 or above is observed in more than two subjects during the study

period in the following categories: gastrointestinal, urinary, with the exception of temporary use of a catheter and urinary incontinence, which can occur after prostatectomy in the absence of radiotherapy.

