**DATA and SAFETY MONITORING:**

The JCCC DSMB meets monthly to review all SAE reports for trials overseen by the JCCC DSMB. All SAE reports, which have been filed since the previous meeting, are presented to the committee for review.

For trials overseen by the JCCC DSMB, the DSMB reviews all dose-limiting toxicities (DLTs) for dose-escalation studies. Protocol suspensions and re-opening of accrual to the next cohort based on DLT evaluation fall under the purview of the DSMB.

For all JCCC oncology trials and TRIO-US studies where the JCCC DSMB has primary oversight, all SAEs shall be reported to the JCCC DSMB in a timely manner [ten days, two days for a death] regardless of relationship and expectedness. The JCCC ORC will review all submissions and the ORC staff will enter the information into the JCCC Clinical Trials database. Reports are generated for full JCCC DSMB review. For trials where the JCCC DSMB has primary DSMB review responsibility, the DSMB requires that the PI generate cumulative adverse event reports for quarterly, biannual or annual review.

The DSMB reviews each SAE report and determines whether or not protocol modifications are warranted to ensure subject safety. In this review, prior occurrences of similar toxicity with the therapy under study are taken into consideration, as well as the severity of the event and the likelihood that it was related to a study drug. The DSMB may recommend no changes to the study if the event is expected or related to other causes such as the subject's underlying condition. The DSMB may request an expert's advice of another non-Principal Investigator with national experience to support their deliberations and decisions.

The JCCC DSMB has the authority to recommend to the UCLA IRB the immediate halt to a study (i.e., discontinuation of any further treatment of enrolled subjects and discontinuation of enrollment of new subjects) should there be any serious unexpected toxicity that warrants further investigation.

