### ***Level of Risk***

#### Level 2

Example of type of trial:

Institutional study for which IND is exempt by FDA or has an IND, but the drug is approved by the FDA for a different indication and is in Phase II or III. Examples are studies using commercially available agents for an unapproved indication based on standard regimen.

- Compliance Officer meets with PI/Staff prior to study initiation; review regulatory requirements and operating system. Compliance Officer provides real time monitoring to determine eligibility prior to enrollment onto the protocol.
- Real time QA monitoring of the subjects and data collection occurs for all subjects entered onto the trial.
- Comprehensive QA auditing within first year or first 10 subjects enrolled, whichever comes first. Subsequent audit frequency will be annually.
- Frequency of DSMB Summary Report is typically on a biannual basis or approximately every six months.

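### The only numeric toxicity stopping rule, most naturally read, exempts urinary incontinence of any grade or duration, so no prespecified number of lasting grade 3+ cases triggers stopping or DSMB review

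*Combined protocol and SAP*

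**What the plan says.** Under Statistical Considerations, the Stopping Rules for Toxicity paragraph gives the only numeric toxicity limit in the plan. The trial stops if related CTCAE v4.0 toxicity of grade 3 or higher, gastrointestinal or urinary, occurs in more than two patients. Two items are carved out: "with the exception of temporary use of a catheter and urinary incontinence, which can occur after prostatectomy in the absence of radiotherapy". The carve-out has no grade limit and no time limit for incontinence.

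The section on prior studies describes a 15-patient trial of preoperative radiotherapy: "Two cases of long-term urinary incontinence were observed. Overall, GU toxicity was within the range expected for adjuvant post-operative RT".

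The Data and Safety Monitoring section adds general safeguards. SAEs go to the DSMB "regardless of relationship and expectedness". The DSMB "determines whether or not protocol modifications are warranted to ensure subject safety", and in doing so "prior occurrences of similar toxicity with the therapy under study are taken into consideration". On timing, "The JCCC DSMB meets monthly to review all SAE reports". Cumulative adverse event reports are also required, at quarterly, biannual or annual intervals. The Level of Risk section adds: "Frequency of DSMB Summary Report is typically on a biannual basis or approximately every six months". None of these provisions states a number of incontinence cases.

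The data needed for a count are already collected. The Follow-up section says "At each follow-up visit, patients are evaluated for CTCAE (version 4.0) toxicity scores", and the assessment table places those visits at 3, 6, 9 and 12 months.

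**The concern.** The reason given for the exemption is that incontinence can follow prostatectomy without radiotherapy. That supports keeping early incontinence out of an automatic stop. It does not support having no count at all for grade 3+ incontinence that is still present months after surgery, when safety is a secondary objective and long-term incontinence is the one late harm that the plan counts in its 15-patient precedent.

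The consequence is limited but real. Lasting severe cases that are not filed as SAEs, or that are filed and judged expected, can accumulate with no stated point at which anyone must look at them together. Two lasting incontinence cases plus one other grade 3 event would not trigger the rule either, because the incontinence cases do not enter its count. The study is also meant to precede the design of a larger trial, so a cumulative judgement on this harm has value after enrollment closes.

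**Working it through.** **Figure to reproduce.** There is none. The plan states no acceptable toxicity rate and no stopping probability for this rule.

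**Inputs from the plan.** 12 patients in 3 years (Study design); a limit of more than two, that is three or more (Stopping Rules); 2 long-term cases among 15 (prior studies); visits every 3 months for a year after surgery, each with a window of 4 weeks either way (Follow-up); monthly DSMB meetings.

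**Assumptions.** True rates of lasting grade 3+ incontinence of 5%, 10%, 13.3% and 30%. The 13.3% is 2/15, with exact 95% CI 1.7% to 40.5%, and treats both precedent cases as grade 3+, which the plan does not say.

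**1. The wording.** "with the exception of temporary use of a catheter and urinary incontinence, which can occur after prostatectomy in the absence of radiotherapy": the adjective at the start attaches to the catheter. Carrying it over to incontinence gives a second, less likely reading, in which only temporary incontinence is exempt. That reading also lacks a time limit.

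**2. Rule as written, natural reading.** The probability that incontinence alone fires it is 0, even at 12 of 12.

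**3. Three or more lasting cases, incontinence alone.** P(X ≥ 3) = 1 − Σ(k=0 to 2) C(n,k) p^k (1−p)^(n−k). For n = 12 and p = 0.05: 1 − (0.5404 + 0.3413 + 0.0988) = 0.020.

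| Patients evaluable | 5% | 10% | 13.3% | 30% |
|---|---|---|---|---|
| 12 (whole study) | 0.020 | 0.111 | 0.208 | 0.747 |
| 9 (36-month accrual) | 0.008 | 0.053 | 0.107 | 0.537 |
| 8 (24-month accrual) | 0.006 | 0.038 | 0.079 | 0.448 |
| 4 (12-month accrual) | 0.000 | 0.004 | 0.009 | 0.084 |

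**4. Where 9, 8 and 4 come from.** With one enrollment every 3 months (months 0, 3, …, 33) and surgery 1 to 2 months after enrollment, patient i reaches the 6-month visit at 3(i−1) + lag + 6. This is before month 33 for i ≤ 9, and stays so with the visit 4 weeks early or late. With a lag of 1.5 months, even accrual over 24 months gives 8 and over 12 months gives 4 (5 if the twelfth patient enrolls exactly at month 12).

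**5. Enrollments affected.** At one patient per 3 months and a 1.5-month lag, the expected number of enrollments that would follow a trigger is Σ(n=3 to 9) P(X_n ≥ 3) = 0.02, 0.15, 0.31 and 1.9 at the four rates.

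**6. Pooled with other events.** Let q be the rate of the other counted grade 3+ events, independent of incontinence. A patient counts with probability u = 1 − (1−q)(1−p). The chance of a review without an automatic stop is P(U ≥ 3) − P(Q ≥ 3), over 12 patients:

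| q | rule as written | pooled, p = 5% | pooled, p = 13.3% | review only, p = 5% | review only, p = 13.3% |
|---|---|---|---|---|---|
| 2% | 0.0015 | 0.045 | 0.267 | 0.044 | 0.265 |
| 5% | 0.020 | 0.105 | 0.358 | 0.085 | 0.339 |
| 10% | 0.111 | 0.247 | 0.511 | 0.136 | 0.401 |

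**7. Waiting time for cases not filed as SAEs.** At one enrollment per 3 months, 6/3 = 2 patients enroll between six-monthly summaries; quarterly reports give 3/3 = 1 and annual reports 12/3 = 4. A trigger tied to the monthly meeting cuts the wait to about one month.

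**8. Precision.** Three of 12 is 25%, with exact 95% CI 5% to 57%.

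**The case against.** The exemption is deliberate and its reason is stated. With 12 patients and no control arm, a count cannot separate surgical from radiation incontinence, so leaving attribution to case review is defensible. This stands as an argument against automatic stopping. It does not argue against a number that calls for a review.

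A reader might infer that no number of lasting cases can ever prompt a DSMB decision. The documents do not support that. A single case filed as an SAE is reported "regardless of relationship and expectedness", and for it the DSMB "determines whether or not protocol modifications are warranted to ensure subject safety". What remains is narrower: the plan does not say whether grade 3 incontinence would be an SAE, and it lets the DSMB recommend no change for an expected event.

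A reader might also take the precedent as evidence of excess harm. It is not. The grade of the two cases is not stated, the technique was mostly conformal without image guidance, and urinary toxicity overall was described as within the expected range.

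The practical gain during enrollment is small: about 0.3 enrollments would follow a trigger at a 13.3% rate, and fewer at lower rates. After enrollment there is nothing left to pause, and the scheduled CTCAE, EPIC and IPSS data would inform a larger trial anyway. Both points stand, and they limit the benefit without removing the gap.

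Finally, a repair that declared all incontinence exempt would settle the ambiguity in the less protective direction and would leave two lasting cases plus one other grade 3 event without any trigger. This objection is right, and it is why the change should limit the exemption in time and pool the counts.

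**Conclusion.** The point holds as a gap in the rule's coverage. On its natural reading, the only numeric toxicity limit never counts urinary incontinence, and no prespecified number of lasting grade 3+ cases leads to stopping or to a DSMB review. Case-by-case SAE review and periodic cumulative or summary reports partly cover this, so the gap is confined to cases not filed as SAEs or set aside as expected. The documents do not show how often either would occur.

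For incontinence alone, the chance of three or more cases in 12 patients runs from 2% at a 5% rate to 75% at 30%. Before the last enrollment, on a three-year accrual, it runs from 1% to 54%. These figures assume independent patients, complete follow-up and the timing set out above, and they are not stopping probabilities for the pooled rule. The change is worth making because it costs little, not because the documents show harm.

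**What to change.** Leave the automatic stopping rule otherwise unchanged, do not widen the exemption, and add wording such as:

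> The exemption covers incontinence before the 6-month visit. Grade 3 or above urinary incontinence present at the 6-month visit or later, whatever the attribution, is counted together with the other grade 3 or above gastrointestinal and urinary events. If lasting incontinence brings that combined count to more than two subjects, the cases go to the DSMB for review at its next monthly meeting; this is a review, not an automatic stop.

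A pause in enrollment during the review is optional. The sponsor may vary the 6-month point and the count. The sponsor should also confirm which reading of the exemption was meant. If only temporary incontinence was to be exempt, lasting related cases already count toward the automatic stop, and the review clause should not replace that.

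**Cost.** A short text addition and no new data: CTCAE is already scored at 6, 9 and 12 months, and the DSMB already meets monthly.

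**Downsides.** Some reviews will concern incontinence due to surgery alone. For incontinence alone, the chance of a trigger over 12 patients is 2% at a true rate of 5% and 11% at 10%, and it is higher once pooled (for example 8.5% for a review without an automatic stop when both rates are 5%). The benefit during enrollment is modest, since about 9 of 12 patients reach six months before the last enrolls if accrual takes 3 years, and fewer if accrual is faster.

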**DATA and SAFETY MONITORING:**

The JCCC DSMB meets monthly to review all SAE reports for trials overseen by the JCCC DSMB. All SAE reports, which have been filed since the previous meeting, are presented to the committee for review.

For trials overseen by the JCCC DSMB, the DSMB reviews all dose-limiting toxicities (DLTs) for dose-escalation studies. Protocol suspensions and re-opening of accrual to the next cohort based on DLT evaluation fall under the purview of the DSMB.

For all JCCC oncology trials and TRIO-US studies where the JCCC DSMB has primary oversight, all SAEs shall be reported to the JCCC DSMB in a timely manner [ten days, two days for a death] regardless of relationship and expectedness. The JCCC ORC will review all submissions and the ORC staff will enter the information into the JCCC Clinical Trials database. Reports are generated for full JCCC DSMB review. For trials where the JCCC DSMB has primary DSMB review responsibility, the DSMB requires that the PI generate cumulative adverse event reports for quarterly, biannual or annual review.

The DSMB reviews each SAE report and determines whether or not protocol modifications are warranted to ensure subject safety. In this review, prior occurrences of similar toxicity with the therapy under study are taken into consideration, as well as the severity of the event and the likelihood that it was related to a study drug. The DSMB may recommend no changes to the study if the event is expected or related to other causes such as the subject's underlying condition. The DSMB may request an expert's advice of another non-Principal Investigator with national experience to support their deliberations and decisions.

The JCCC DSMB has the authority to recommend to the UCLA IRB the immediate halt to a study (i.e., discontinuation of any further treatment of enrolled subjects and discontinuation of enrollment of new subjects) should there be any serious unexpected toxicity that warrants further investigation.

Requests for single subject exceptions/waivers from the approved study protocol, including out of window procedures and eligibility deviations, must be reviewed and approved by a member of the DSMB. Each trial is assigned a primary and secondary reviewer who is responsible for reviewing each exception/waiver request for that trial. Approvals and disapprovals of the request are sent to the Principal Investigator via email and copied to the UCLA IRB. Requests for single subject exceptions/waivers are made by the Principal Investigator via email utilizing the "Single Subject Exception

Request Form.”

JCCC DSMB correspondences are addressed to the Principal Investigator and copied to the UCLA IRB. Minutes of the DSMB meetings are maintained in a computer file.

Confidentiality: Each member of the JCCC DSMB is responsible for maintaining strict confidentiality of the study data. Members will not share any study data or information about the study with any individual external to the JCCC DSMB or the statistical working group for the study. The DSMB members may contact the statistical working group directly with questions regarding the operational details associated with the data analysis and summary presentations. Communication of deliberations or recommendations of the JCCC DSMB, either written or oral, should not be made outside of the Committee or the statistical working group. Outcome results are strictly confidential and must not be divulged to any non-member of the JCCC DSMB except in those cases where DSMB is required to inform the UCLA IRB of its determinations. Disclosure of outcome results to the IRB must only occur with written approval of the DSMB. A member who believes he or she may have a potential intellectual or financial conflict of interest during the course of review of the data must inform the chairperson of the DSMB. In such case, the meeting minutes will record the disclosure of the potential conflict of interest and that the individual recuse himself from the discussions and abstains from voting on the DSMB decision.

#### Level of Risk of a Study

All interventional clinical trials undergo scientific review by the Internal Scientific Peer Review Committee (ISPRC) which requires that a Data and Safety Monitoring Plan is in place before a trial can be approved to begin. For trials overseen by the JCCC DSMB, the JCCC DSMB will determine the degree of risk of the study and will ensure that there are procedures in place to ensure the safety of the subjects that are enrolled in the trial. The intensity level of study oversight is determined by the risk category. Some of the factors that are considered when assigning the Level of Risk category include:

- A biostatistical design and appropriate procedures for proper data management so that the information collected can be properly validated.
- Appropriate Serious Adverse Event reporting procedures must be in place.
- The study duration must be appropriate and must be based on a realistic rate of enrollment.
- Data collection and data management must be adequate to verify and ensure subject eligibility.

## **Assignment of risk**

Assigning risk ensures that the data and safety monitoring is based on the level of risk (low, medium, or high) to ensure that the data and safety monitoring activities are appropriate. Below are some of the criteria used to make a decision regarding the assignment of risk:

- Expected duration of the study based upon the estimated rate of enrollment.
- Type of study population (e.g., children, geriatric)
- The procedures used in the trial are commensurate with the degree of risk.
- Adequate data management systems in place and appropriate case report forms
- Proper serious adverse event reporting procedures in place
- Proper biostatistical design and data analysis procedures in place.

### ***Level of Risk***

#### Level 2

Example of type of trial:

Institutional study for which IND is exempt by FDA or has an IND, but the drug is approved by the FDA for a different indication and is in Phase II or III. Examples are studies using commercially available agents for an unapproved indication based on standard regimen.

- Compliance Officer meets with PI/Staff prior to study initiation; review regulatory requirements and operating system. Compliance Officer provides real time monitoring to determine eligibility prior to enrollment onto the protocol.
- Real time QA monitoring of the subjects and data collection occurs for all subjects entered onto the trial.
- Comprehensive QA auditing within first year or first 10 subjects enrolled, whichever comes first. Subsequent audit frequency will be annually.
- Frequency of DSMB Summary Report is typically on a biannual basis or approximately every six months.

